8.1. Permitted Concomitant Medications and Procedures

Subjects with myeloma-associated bone disease may receive bisphosphonate therapy prior to study entry, unless such therapy is contraindicated. The use of bisphosphonates is permitted throughout the study.

Platelet/RBC transfusions and hematopoietic growth factors are also permitted during the study. However, prophylactic use of transfusions or hematopoietic growth factors to prevent a potential DLT should be avoided unless deemed medically necessary by the treating physician for subject safety.

Concurrent use of hormones for noncancer-related conditions (eg, insulin for diabetes and hormone replacement therapy) is acceptable.

8.2. Prohibited Concomitant Medications and Procedures

The following medications are considered exclusionary during the study. The sponsor must be notified if a subject receives any of these during the study.

- 1. The prophylactic use of hematopoietic growth factors or platelet/RBC transfusions will not be allowed during the first cycle (DLT evaluation period); however, it is permitted at the Investigator's discretion after a subject completes the first cycle or within the first cycle if a hematological DLT has already been declared for that subject. Subjects who fail absolute neutrophil count, hemoglobin or platelet eligibility criteria at screening should not be retested for the study after being treated with growth factors or platelet/RBC transfusion.
- 2. Any investigational anticancer therapy.
- 3. Any concurrent chemotherapy, radiotherapy (except palliative radiotherapy), immunotherapy, biologic or hormonal therapy for cancer treatment.
- 4. Immunosuppressive medications including, but not limited to systemic corticosteroids at doses exceeding 10 mg/day of prednisone or equivalent, methotrexate, azathioprine, and tumor necrosis factor alpha (TNF-α) blockers. Pre- and post-infusion medication for infusion reaction prophylaxis as outlined in Table 6 is permitted. Use of

immunosuppressive medications for the management of IP-related AEs or in subjects with contrast allergies is acceptable. In addition, use of inhaled, topical, intranasal corticosteroids or local steroid injections (eg, intra-articular injection) is permitted. Temporary uses of corticosteroids for concurrent illnesses (eg, food allergies, CT scan contrast hypersensitivity, moderate to severe infusion-related reactions, etc) are acceptable upon discussion and agreement with the medical monitor.

- 5. Live attenuated vaccines during the study through 30 days after the last dose of durvalumab.
- 6. Herbal and natural remedies are to be avoided.
- 7. Strong inhibitors of CYP1A2 (eg, ciprofloxacin, enoxacin, and fluvoxamine) should be avoided for subjects receiving POM.

8.3. Required Concomitant Medications and Procedures

- **Infusion reaction prophylaxis:** Guidance on preinfusion and postinfusion medications for infusion reaction prophylaxis in relation to DARA dosing is detailed in Table 6.
- Antiviral prophylaxis: All subjects must initiate antiviral prophylaxis to prevent herpes zoster reactivation within 1 week of starting DARA and continue for 3 months following last dose of DARA.
- Thromboembolism prophylaxis: low-dose aspirin, low molecular weight heparin, or other equivalent antithrombotic or anticoagulant will be given to all subjects who receive POM as a part of study treatment.

9. STATISTICAL CONSIDERATIONS

9.1. Overview

All analyses will use descriptive statistics. The analyses will be done by cohorts and arms. Subjects treated with the recommended dose in the Phase 2 portion of D^2 will be combined with the corresponding dose cohort in the safety run-in phase as one single dose cohort for efficacy and safety analysis. Safety and efficacy data for subjects after addition of POM + dex following confirmed PD will be analyzed separately.

9.2. Study Population Definitions

The following 5 populations will be used for analysis:

- Safety Population: all enrolled subjects who take at least 1 dose of any study treatment. All safety analyses will be based on this population
- Dose-limiting Toxicity Evaluable Population: all subjects from the Safety Population who meet the minimum exposure criterion and have sufficient safety evaluations, or experience a DLT during the first treatment cycle.
- Full Analysis Population: all subjects who are enrolled in this study.
- Efficacy Evaluable (EE) Population: all enrolled subjects who take at least 1 dose of study treatment and who have measurable disease at baseline and at least one postbaseline efficacy assessment.
- Pharmacokinetic Population: includes all subjects who receive at least 1 dose of study treatment and have at least 1 measureable plasma exposure. If any subjects are found to be noncompliant with respect to dosing, have incomplete data, or encounter other circumstances that would affect the evaluation of the PK, a decision will be made on a case-by-case basis as to the inclusion of his PK data in the statistical analysis.

9.3. Sample Size and Power Considerations

Sample size for D^2 arm is calculated based on Simon's 2-stage design (Simon, 1989). The null hypothesis that the true overall response rate (ORR) is < 30% will be tested against a one-sided alternative. In the first stage, 32 subjects will be accrued. If there are 11 or fewer responses in these 32 subjects (11/32 = 34.4%), the study will be stopped. Otherwise, 68 additional subjects will be accrued to a total of 100. The null hypothesis will be rejected if 39 or more responses are observed in 100 subjects (39/100 = 39%). This design yields a Type I error rate of 0.05 and power of 80% when the true overall response rate is 45%.

Number of observed responses in 32 subjects	80% Confidence Interval
10/32	31.3% (20.4%, 44.0%)
11/32	34.4% (23.1%, 47.2%)
12/32	37.5% (25.9%, 50.4%)
13/32	40.6% (28.7%, 53.5%)
14/32	43.8% 31.6%, 56.6%)
15/32	46.9% (34.6%, 59.6%)
16/32	50.0% (37.4%, 62.6%)
17/32	53.1% (40.4%, 65.5%)
18/32	56.3% (43.4%, 68.4%)
19/32	59.4% (46.5%, 71.3%)
20/32	62.5% (49.6%, 74.1%)

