- Clinical laboratory evaluations
- Pregnancy testing/counseling
- Electrocardiogram (ECG)
- Concomitant medications and procedures
- Adverse events (AEs)
- Second primary malignancies

Pharmacokinetic

 Serum/plasma samples will be collected to assay plasma concentrations of DURVA and DARA

Other

• Eastern Cooperative Oncology Group (ECOG) Performance Status

Statistical Methods

Simon's 2-stage design (Simon, 1989) will be used. The null hypothesis that the true overall response rate (ORR) is < 30% will be tested against a one-sided alternative. In the first stage, 32 subjects will be accrued. If there are 11 or fewer responses in these 32 subjects (11/32 = 34.4%), the study will be stopped. Otherwise, 68 additional subjects will be accrued to a total of 100. The null hypothesis will be rejected if 39 or more responses are observed in 100 subjects (39/100 = 39%). This design yields a Type I error rate of 0.05 and power of 80% when the true overall response rate is 45%. All analyses will use descriptive statistics. No formal statistical comparison/testing will be performed.

TABLE OF CONTENTS

TITLE P.	AGE	1
PROTOC	COL SUMMARY	6
1.	INTRODUCTION	18
1.1.	Disease Background	18
1.2.	Compound Background	18
1.2.1.	Durvalumab (MEDI4736)	18
1.2.2.	Daratumumab	19
1.2.3.	Pomalidomide	19
1.3.	Rationale	19
1.3.1.	Study Rationale and Purpose	19
1.3.2.	Rationale for the Study Design	20
1.3.4.	Rationale for Choice of Combination Compounds	22
1.5.4.	Rationale for Choice of Combination Compounds	
2.	STUDY OBJECTIVES AND ENDPOINTS	24
3.	OVERALL STUDY DESIGN	26
3.1.	Study Design	26
3.1.1.	D ² Arm	
3.1.1.1.	D ² Safety Run-In Phase	26
3.1.1.2.	D ² Phase 2 Portion	27
3.1.1.3.	Addition of Pomalidomide Plus Dexamethasone to Daratumumab Plus Durvalumab Upon Progressive Disease	27
3.1.3.	Dose Review Team.	27
3.1.4.	Dose-limiting Toxicity.	
3.2.	Study Duration for Subjects	
3.3.	End of Trial	
1	STUDY POPUL ATION	33

Durvalumab (MEDI4736)

Protocol 1	MEDI4736-MM-003	Celgene Corporation
4.1.	Number of Subjects	33
4.2.	Inclusion Criteria	33
4.3.	Exclusion Criteria	34
5.	TABLE OF EVENTS	38
6.	PROCEDURES	45
6.1.	Screening Period.	45
6.2.	Treatment Period	47
6.2.1.	End of Treatment	48
6.3.	Follow-up Period	49
6.3.1.	Safety Follow-up	49
6.3.2.	Second Primary Malignancy Follow-up	50
6.4.	Efficacy Assessments	50
6.4.1.	Laboratory Assessments for Efficacy Parameters	50
6.4.2.	Bone Marrow Aspiration and/or Biopsy	51
6.4.3.	Bone Lesion Assessment	51

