1. INTRODUCTION

On 05 Sep 2017, a Partial Clinical Hold was placed on this study by the United States (US) Food and Drug Administration (FDA). The decision by the FDA was based on data related to risks of anti-programmed cell death-1 (PD-1) antibody, pembrolizumab, in combination with immunomodulatory drugs (IMiDs®) in patients with multiple myeloma. As a result, enrollment into this study has been discontinued. Subjects who are receiving clinical benefit, based on the discretion of the investigator, may remain on study treatment after being reconsented.

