9.8. Efficacy Analysis

9.8.1. Response (International Myeloma Working Group Criteria)

Tumor response, including PD, will be assessed by the investigators using the International Myeloma Working Group Criteria (IMWG) criteria.

The ORR will be calculated as the percent of responders (count of subjects with at least a PR, divided by the number of subjects in the EE Population). The ORR together with the proportions in each response category based on the IMWG criteria (ie, CR, Very Good Partial Response [VGPR], PR, Stable Disease [SD], and Progressive Disease [PD]) will be tabulated by dose cohort and arm. A 95% confidence interval of the ORR of D² for all subjects treated with the RP2D

All response related analysis will be carried out for the efficacy evaluable population

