9.10. Interim Analysis

The Phase 2 portion of this study uses the Simon's 2-stage design (Simon, 1989). Once the RP2D is confirmed after the safety run-in portion, a cohort of 32 subjects (including subject enrolled in the safety run-in portion) will be enrolled at the RP2D to determine the safety and preliminary efficacy of D². If there are 11 or fewer responses in these 32 subjects (11/32=34.4%), the study will be stopped. Otherwise, 68 additional subjects will be accrued for a total of 100.

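### The stated Type I error of 0.05 is not that of the written one-sided Simon rule, whose exact value is 0.0247; the stated 80% power is correct

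*Combined protocol and SAP*

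**What the plan says.** Section 9.3 defines the design completely, and the Statistical Methods part of the Protocol Summary repeats it.

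- Hypothesis: "The null hypothesis that the true overall response rate (ORR) is < 30% will be tested against a one-sided alternative".
- Stage 1: "In the first stage, 32 subjects will be accrued". Section 9.10 gives the same interim rule: "If there are 11 or fewer responses in these 32 subjects (11/32=34.4%), the study will be stopped".
- Stage 2: 68 more subjects, 100 in total.
- Final rule: "The null hypothesis will be rejected if 39 or more responses are observed in 100 subjects (39/100 = 39"%).
- Claimed properties: "This design yields a Type I error rate of 0.05 and power of 80% when the true overall response rate is 45"%.

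Three other statements bear on the point. The Protocol Summary adds "No formal statistical comparison/testing will be performed". Section 9.8.1 calculates the ORR as responders "divided by the number of subjects in the EE Population", a population that can be smaller than the number enrolled. Section 1 reports the partial clinical hold and says "As a result, enrollment into this study has been discontinued".

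**The concern.** A Simon rule is fixed by four integers: the two sample sizes and the two cutoffs. Once these are written down, the Type I error and the power follow exactly from the binomial distribution. The plan gives all four integers and both properties, so the properties can be checked directly, and only one of them agrees with the rule.

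The Type I error is the figure by which a reader judges a rejected null hypothesis. If it does not match the rule printed beside it, someone reporting or checking the design cannot tell whether the error rate or the cutoffs are wrong. They might conclude that a cutoff was mistyped, or that 100 subjects were needed for a one-sided 0.05 test, which is not so.

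**Working it through.** **Inputs (Section 9.3; interim rule confirmed in Section 9.10).** n1 = 32, stop if X1 ≤ 11; n2 = 68, n = 100, reject if X1 + X2 ≥ 39; null boundary p0 = 0.30, alternative p1 = 0.45, one-sided. It is assumed that all 32 and all 100 subjects count in the denominator.

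**Formula.** The probability of rejecting at a true response rate p is

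P(reject | p) = Σ (x = 12 to 32) P[Bin(32, p) = x] × P[Bin(68, p) ≥ 39 − x]

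It increases with p, so its maximum under the null is at p = 0.30.

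**Results for the written rule**

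| Quantity | Stated | Exact |
|---|---|---|
| Power at p = 0.45 | 80% | 0.8001 |
| Type I error at p = 0.30 | 0.05 | 0.0247 |
| P(stop at Stage 1), p = 0.30 | not given | 0.7717 |
| P(stop at Stage 1), p = 0.45 | not given | 0.1513 |

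The power is reproduced, which indicates that the rule has been read as the authors meant it. The Type I error is not: 0.05 / 0.0247 = 2.02.

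**Other readings that might give 0.05**

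1. Stage 1 stop ignored: P[Bin(100, 0.30) ≥ 39] = 0.0340.
2. Final cutoff misprinted, same Stage 1: reject at ≥ 38 gives 0.0364; reject at ≥ 37 gives 0.0514. The value passes from below 0.05 to above it without meeting it.
3. Normal approximation for 39/100, single stage: 0.0248 without and 0.0318 with continuity correction.
4. Fewer evaluable subjects (the Section 9.8.1 denominator), with the response counts 11 and 39 unchanged. The plan gives no such sizes, so these are assumed for illustration:

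| Evaluable at Stage 1 / in total | Type I error at 30% | Power at 45% |
|---|---|---|
| 32 / 100 | 0.0247 | 0.800 |
| 31 / 97 | 0.0148 | 0.738 |
| 30 / 95 | 0.0099 | 0.678 |
| 28 / 90 | 0.0033 | 0.520 |

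Each loss of evaluable subjects moves the Type I error further from 0.05.

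5. Doubled for two sides: 2 × 0.02473 = 0.0495, which rounds to 0.05.

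**Where the rule probably comes from.** A search over two-stage designs with p0 = 0.30, p1 = 0.45 and power of at least 80% gives:

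| One-sided limit | Criterion | Stop at | Reject at | Type I error | Power | Expected N at 30% |
|---|---|---|---|---|---|---|
| 0.025 | Smallest expected N | ≤ 11/32 | ≥ 39/100 | 0.0247 | 0.800 | 47.5 |
| 0.05 | Smallest expected N | ≤ 9/27 | ≥ 31/81 | 0.0499 | 0.802 | 41.7 |
| 0.05 | Smallest maximum N | ≤ 16/46 | ≥ 26/65 | 0.0500 | 0.803 | 49.6 |

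The first row is exactly the written rule; its expected N is 32 + (1 − 0.7717) × 68 = 47.5. A one-sided 0.05 target would have needed 81 subjects at most (or 65), not 100.

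**The case against.** The strongest reply is that 0.05 is not false if read as an upper limit, since 0.0247 is below it, and that only a label is missing. Section 9.8.1 plans a 95% confidence interval for the ORR, whose lower limit corresponds to one-sided 0.025, so the rule and the reporting could be seen as consistent.

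Part of this stands. As a bound, 0.05 is true, and the planned 95% interval is mild evidence that one-sided 0.025 was meant. But the text says what the design yields and puts the figure beside a power that is the attained value, so a reader will take both the same way. A cutoff of 38 would also satisfy a 0.05 limit (0.0364) with more power (0.8185), so a bound of 0.05 does not explain the choice of 39. Nor does the interval settle the matter: ignoring the stages, the exact tail for 39 of 100 is 0.0340, above 0.025, so an exact 95% interval at 39 responses would still include 30%.

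Two further reservations are fair. The intended level is inferred from a design search, not from any statement in the plan. And the 80% power holds only with full evaluability, as the table of smaller denominators shows.

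The practical stakes are also small. The error is conservative, the Protocol Summary disclaims formal testing, and enrollment has been discontinued. This limits the importance of the correction but does not make the stated figure right.

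**Conclusion.** The point holds. The written one-sided rule has an exact Type I error of 0.0247, not 0.05; the stated value is 2.02 times the attained one. The stated 80% power is right (0.8001). Both figures assume that all 32 and all 100 subjects are in the denominator; fewer evaluable subjects with the same counts would lower both.

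The most likely explanation is a design built for one-sided 0.025 and described by its two-sided equivalent of 0.05. That is an inference, but the value 0.0247 does not depend on it. This is a wrong stated property and not a fault in the thresholds, the sample size or the power. The true false-positive risk is lower than the plan says. It should be corrected, mainly so that the design is reported accurately.

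**What to change.** In Section 9.3 and in the Statistical Methods part of the Protocol Summary, replace the Type I error of 0.05 with a one-sided Type I error rate of 0.025 (exact 0.0247). Keep the cutoffs, the sample size and the power as written. The sponsor should confirm the nominal level; the cutoffs would need restating only if one-sided 0.05 was in fact intended.

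The cost is one phrase in two places. Sample size, analysis programs and conduct do not change. If the study report or a publication describes the design, it should carry the corrected figure.

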9.4. Background and Demographic Characteristics

Summaries for the demographics and baseline characteristics will be carried out for each dose cohort and overall for the full analysis population. Age, height, weight, and other continuous baseline disease characteristics will be summarized using descriptive statistics, while gender, race, and other categorical variables will be provided using frequency tabulations.

9.5. Medical History

Medical history data will be summarized for full analysis population using frequency tabulations by the Medical Dictionary for Regulatory Activities (MedDRA) Version 18 or higher system organ class and preferred term.

9.6. Concomitant Medications and Procedures

All concomitant medications and procedures documented during the study will be summarized for full analysis population using frequency tabulations. The Anatomical Therapeutic Chemical (ATC) coding scheme of the World Health Organization (WHO) will be used to group medications into relevant categories for these tabulations.

9.7. Subject Disposition

Subject disposition (analysis population allocation, entered, discontinued, along with primary reason for discontinuation) will be summarized for full analysis population using frequency and percent by treatment arm and dose cohort and follow-up phases. A summary of subjects enrolled by site will be provided. Protocol deviations will be summarized using frequency tabulations.

9.8. Efficacy Analysis

9.8.1. Response (International Myeloma Working Group Criteria)

Tumor response, including PD, will be assessed by the investigators using the International Myeloma Working Group Criteria (IMWG) criteria.

The ORR will be calculated as the percent of responders (count of subjects with at least a PR, divided by the number of subjects in the EE Population). The ORR together with the proportions in each response category based on the IMWG criteria (ie, CR, Very Good Partial Response [VGPR], PR, Stable Disease [SD], and Progressive Disease [PD]) will be tabulated by dose cohort and arm. A 95% confidence interval of the ORR of D² for all subjects treated with the RP2D

All response related analysis will be carried out for the efficacy evaluable population

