4. STUDY POPULATION

4.1. Number of Subjects

Up to approximately 144 subjects with RRMM will be enrolled worldwide.

• D² Cohort: Run-in cohort up to 18; Simon Stage 1 up to 26; Simon Stage 2 up to 68

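### The primary ORR drops dosed subjects who have no post-baseline assessment, so it can only equal or exceed the all-treated rate, which the plan does not report

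*Combined protocol and SAP*

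**What the plan says.** ORR is a primary endpoint (Table 2). Section 9.8.1 calculates it as the "count of subjects with at least a PR, divided by the number of subjects in the EE Population" and closes with "All response related analysis will be carried out for the efficacy evaluable population".

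Section 9.2 admits to the EE Population enrolled subjects with at least one dose "who have measurable disease at baseline and at least one postbaseline efficacy assessment". The same section defines two wider sets: the Safety Population (at least one dose) and the Full Analysis Population (everyone enrolled). Neither is used for response. PFS in Section 9.8.4 does use the Full Analysis Population.

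The investigator assesses response from Cycle 2, on Day 1 of each cycle and at EOT (Section 6.4.5). Footnote a of Appendix B requires two consecutive assessments for every response category from PR upward.

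The Simon rule is worded in subjects accrued. Section 9.3 stops the study "If there are 11 or fewer responses in these 32 subjects", and otherwise accrual goes on to 100. Section 9.10 repeats the rule for 32 subjects enrolled at the RP2D.

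**The concern.** A subject who is dosed and then dies, withdraws or is lost before any efficacy assessment is a treatment failure for the purpose of a response rate. Under Section 9.8.1 that subject is not counted at all. The numerator is the same with or without such subjects, and only the denominator shrinks, so the departure from the all-treated rate always goes one way.

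This matters because the ORR is likely to be read as the main efficacy result. Enrollment was discontinued after the partial clinical hold (Protocol Summary, Sections 1 and 3.2), and Section 9.1 describes all analyses as descriptive. A reader will look at the estimate and its interval more than at a test. In a sample smaller than the planned 100, each excluded subject also moves the percentage more.

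**Working it through.** **Inputs.** Denominator and numerator: Section 9.8.1. EE conditions: Section 9.2. Confirmation of response: Appendix B. Stage sizes and cut-offs (stop at 11 or fewer of 32; reject at 39 or more of 100; 30% against 45%): Section 9.3. The number of treated subjects with no post-baseline assessment, k, is not given anywhere. It is assumed here to be 0 to 3 in 32.

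**Step 1: reproduce the plan's own figures.** With X1 the responses in the first 32 subjects and X2 those in the next 68, the probability of rejecting is the sum over x1 = 12 to 32 of P(X1 = x1) × P(X2 ≥ 39 − x1).
- At 45% this gives 0.8001, against the stated power of 80%.
- At 30% it gives 0.0247, against the stated Type I error of 0.05. The attained error is below the stated level. That is a separate matter and plays no part in this point.

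The 80% intervals tabulated in Section 9.3 are Clopper-Pearson intervals, agreeing within 0.1 percentage point after rounding. For 12 of 32 the calculation gives 25.9 to 50.4, as printed. The method for the 95% interval is not legible in Section 9.8.1, so the same exact method is assumed below.

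**Step 2: direction.** Let R be the responders among N treated subjects, of whom k have no post-baseline assessment. None of the k can be among the R. Then:
- all-treated ORR = R / N
- EE-based ORR = R / (N − k) = (R / N) × N / (N − k)

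The factor N / (N − k) is never below 1. The two rates are equal only if k = 0 or R = 0.

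**Step 3: size, at the Stage 1 sample size with 12 responders.**

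| Unassessed k | Denominator | ORR | Exact 95% CI |
|---|---|---|---|
| 0 | 32 | 12/32 = 37.5% | 21.10 to 56.31 |
| 1 | 31 | 12/31 = 38.7% | 21.85 to 57.81 |
| 2 | 30 | 12/30 = 40.0% | 22.66 to 59.40 |
| 3 | 29 | 12/29 = 41.4% | 23.52 to 61.06 |

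Each excluded subject adds about 1.2 to 1.4 percentage points (38.7 − 37.5 = 1.2; 41.4 − 40.0 = 1.4).

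**Step 4: the Simon decision.** The rule counts responses among 32 and then 100 accrued subjects. An unassessed subject is one of the 32 or the 100 and contributes no response. The thresholds of 12 and 39 are reached or missed exactly as before, and 0.0247 and 0.8001 do not change.

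**The case against.** The best reply is that k may be close to zero. Section 6.2.1 requires an EOT evaluation within 7 days of the decision to stop, whatever the reason, and Section 6.4.1 places efficacy laboratory tests there. Many early leavers will therefore stay in the EE Population as non-responders. The Protocol Summary also lists corrected serum calcium among the key efficacy assessments, and the chemistry panel is drawn on several days of Cycle 1. Read literally, that would keep still more subjects in, although Section 6.4.1 ties calcium as an efficacy measure to Day 1 of each cycle and EOT. Section 9.7 also tabulates "analysis population allocation, entered, discontinued, along with primary reason for discontinuation", so the number excluded will be visible. All of this limits the size. It does not change the direction, and a disposition count does not correct the primary estimate as the plan defines it.

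Five stronger readings are tempting, and the documents do not support them.

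- **That the 95% CI uses a different group.** Section 9.8.1 refers to an interval "for all subjects treated with the RP2D", but the sentence is cut off in the available text. Its legible words fit the pooled RP2D dose cohort of Section 9.1, with the next sentence naming EE as the analysis set. No conflict is shown.
- **That the Simon error rates are inflated.** Sections 9.3 and 9.10 count accrued or enrolled subjects, not evaluable ones.
- **That Section 4.1 independently confirms the stage sizes.** It gives "Simon Stage 1 up to 26; Simon Stage 2 up to 68", but also a run-in of up to 18 and about 144 subjects in all. It does not itself yield 6 + 26 = 32.
- **That the response table is defective because it lists only "CR, Very Good Partial Response [VGPR], PR, Stable Disease [SD], and Progressive Disease [PD"].** With an EE denominator every subject has been assessed, and SD takes in those meeting no other category. A not-evaluable row is needed only once the denominator changes.
- **That every EE exclusion raises the ORR.** The exact relation covers unassessed subjects only. A subject excluded for lacking measurable disease could in principle respond under the marrow criterion of Appendix B. Inclusion criterion 2 and exclusion criterion 14 should make such subjects rare.

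**Conclusion.** The point holds for the estimate, not for the decision rule. As defined, the primary ORR leaves out dosed subjects who were never assessed. It therefore equals or exceeds the all-treated rate, and no all-treated ORR is planned beside it. If the interval is also computed on EE, as the closing sentence of Section 9.8.1 directs, it shifts upward too.

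The size rests on an assumed k. At 32 treated subjects with 12 responders, one or two exclusions move 37.5% to 38.7% or 40.0%, within an interval about 35 points wide (56.3 − 21.1 = 35.2). The effect is modest, and it is nil if every dosed subject has an assessment. This is a cheap improvement to the definition of a primary endpoint, not a flaw that undermines the design.

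**What to change.** In Section 9.8.1, define the primary ORR and its 95% CI on all subjects who received at least one dose of study treatment at the RP2D. Count subjects with no post-baseline assessment as non-responders and show them as not evaluable in the response table. Keep the EE-based ORR as a sensitivity analysis.

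The cost is a change of wording in Section 9 and one table row. No new data are needed. The only downside is that the reported ORR may be slightly lower.
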